3.2 STUDY TREATMENT

The patients will be assigned to one of two treatment group in 1:1 ratio:

- Group 1. OKITASK® 40 mg – 35 patients
- Group 2. Placebo – 35 patients

The patient will assess pain by VAS at 0' – immediately before study drug dosing.

Upon study drug administration the patients will immediately start two stopwatches. One of them will be stopped once the patient feels first perceptible pain relief; the second one will be stopped once the patient feels the meaningful pain relief.

The patient will stay at the site for 6 hours post-dose for pain and AE assessment. Pain intensity will be assessed by VAS at 5', 10', 15', 30', 45', 60' (1 hour), 90' (1.5 hours), 120' (2 hours), 180' (3 hours), 240' (4 hours), 300' (5 hours), and 360' (6 hours) post-dose.

Pain relief will be assessed by VAS at 5', 10', 15', 30', 45', 60' (1 hour), 90' (1.5 hours), 120' (2 hours), 180' (3 hours), 240' (4 hours), 300' (5 hours), and 360' (6 hours) post-dose.

Patients should mark actual time points of VAS measurement. Deviations from planned time points will not be considered as protocol deviations. Only omitted values will be considered as protocol deviations.

Patients' overall assessment will be performed right before the discharge from the site.

Follow-up phone call to the patient to assess AEs will be performed on Day 3 (48 hours

after the study drug dosing). Any SAE spontaneously reported by the patient within 30 days of dosing will be collected.

Should the patient require rescue medication at any time during 6 hours post-dose, the last VAS measurement and patient's overall assessment will be performed before the rescue medication dosing.

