6. DETERMINATION OF SAMPLE SIZE¹

Sample size calculation was based on the paper of Seymour 1996 [3] concerning a randomized, double-blind, placebo-controlled study of treatment with placebo, paracetamol (500 and 1000 mg) and ketoprofen (12.5 and 25 mg).

The unadjusted AUC_{0-6h} values for placebo and ketoprofen were about 263 and 173 mmh⁻¹, respectively. The corresponding SD were 106 mm h⁻¹ (about 40% of the mean value for placebo AUC) and 121 mmh⁻¹ (about 70% of the mean value for ketoprofen 25 mg AUC).

The testing hypothesis for this trial is the superiority of ketoprofen versus placebo that in statistical term is:

H_0 : mean of placebo \geq mean of ketoprofen (no difference between treatments)

H_1 : mean of placebo $<$ mean of ketoprofen (clinically and statistically significant difference between the groups) $\Delta=90$ mm h⁻¹

A total of 58 subjects (29 subjects per group) will be necessary to assess a difference of 90 mm h⁻¹ between the groups with a power of 80%, $\alpha = 0.05$, SD=121 mmh⁻¹, and randomization rate of 1:1. Sample size calculation was performed using SAS 9.2².

Assuming a drop-out rate of 15%, 70 subjects in total (35 subjects per group) should be enrolled. Considering the screen-failure rate of about 30%, up to 100 patients will be screened in the study.

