9.2 DEMOGRAPHICS AND BASELINE CHARACTERISTICS

Demographic data and baseline characteristics will be presented using descriptive statistic for the ITT analysis populations.

Following parameters will be presented at screening:

- Age
- Gender
- Height
- Weight
- BMI
- Race
- Medical history
- Concomitant diseases
- Previous therapy
- Pregnancy test (for females)
- Oral cavity examination (only abnormal parameters)
- Vital signs (only abnormal parameters)

Between groups comparisons will be performed for:

- Age (ANOVA from LME model)
- Gender

¹ Baseline is Day 1 time 0 minutes

Number and percent of patients with previous medications will be presented as a frequency arrays by ATC (3 and 5 levels) and treatment groups.

Current and history diagnoses will be coded by MEDDRA dictionary. Data will be presented by SOC (System Organ Class) and PT (Preferred Term).

Frequencies of CS¹ oral cavity examination abnormalities at Day 1 will be summarized with descriptive statistics (absolute and relative frequencies). Table will show only CS abnormalities. No between group tests are planned.

Frequencies of CS vital signs abnormalities at Day 1 will be summarized with descriptive statistics (absolute and relative frequencies). Table will show only CS abnormalities. No between group tests are planned.

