10.1 PRIMARY EFFICACY VARIABLE

Primary variable will be the AUC_{0-6h} without or with LOCF of pain intensity profile between time 0 (baseline value of VAS) and 6 hours post-treatment. AUC_{0-6h} analysis will be based on **actual rather than scheduled timings** and will be calculated using the trapezoidal rule:

$$\sum \frac{P_n + P_{n-1}}{2} (t_n - t_{n-1})$$

where, P_n – pain intensity at point n, t_n – time point n.

Treatment AUCs will be compared using ANOVA methodology (simple GLM model). In case of significant covariates discovered during baseline data analysis, such covariates could be added to the ANOVA model (level to stay 0.15). F-test for type III treatment effect will be used for testing the Null hypothesis.

Null hypothesis (H_0) that OKITASK® is no different from Placebo will be rejected and alternative hypothesis (H_1) that OKITASK® is superior to Placebo will be accepted if mean AUC_{0-6h} (OKITASK®) is less than mean AUC_{0-6h} (Placebo) and $p < 0.05$.

$$H_0: \mu_T = \mu_R$$

$$H_1: \mu_T \neq \mu_R$$

where μ_T – OKITASK® (**Test**) mean AUC_{0-6h} ; μ_R – Placebo (**Reference**) mean AUC_{0-6h} .

If the actual time is not recorded, the scheduled time will be used instead. LOCF approach will be applied as described in Section 7.

Additional test on FCS replaced data will be performed to confirm analysis of the LOCF data (sensitivity).

For the PP population data could not be missing. There were no LOCF or other methods applied.

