12.2.2 Secondary efficacy

Table 12.13 secondary efficacy. Visual Analogue Scale. Pain Intensity Assessment with LOCF. ITT population. N = XX

Parameter Treatment	Result				
	N	Mean (SD)	Median	Min	Max
Visual Analogue Scale. Pain Intensity. AUC_{0-6h}. LOCF					
OKITASK [®]	XX	XX.X (XX.X)	XX.X	XX.X	XX.X
PLACEBO	XX	XX.X (XX.X)	XX.X	XX.X	XX.X
p-value ANOVA = 0.***					
Visual Analogue Scale. Pain Intensity. AUC_{0-6h}. Multiple Imputation					
OKITASK [®]	XX	XX.X (XX.X)	XX.X	XX.X	XX.X
PLACEBO	XX	XX.X (XX.X)	XX.X	XX.X	XX.X
p-value ANOVA = 0.***					

Table 12.14 secondary efficacy. Visual Analogue Scale. Pain Intensity Assessment with LOCF. ITT population. N = XX

Parameter Treatment	Result				
	N	Mean (SD)	Median	Min	Max
Visual Analogue Scale. Pain Intensity. AUC_{0-6h}. LOCF					
OKITASK [®]	XX	XX.X (XX.X)	XX.X	XX.X	XX.X
PLACEBO	XX	XX.X (XX.X)	XX.X	XX.X	XX.X
p-value ANOVA = 0.***					
Visual Analogue Scale. Pain Intensity. AUC_{0-6h}. Multiple Imputation					
OKITASK [®]	XX	XX.X (XX.X)	XX.X	XX.X	XX.X
PLACEBO	XX	XX.X (XX.X)	XX.X	XX.X	XX.X
p-value ANOVA = 0.***					

Table 12.15 Secondary efficacy. Visual Analogue Scale. Pain Intensity profile. ITT population. N = XX

Parameter Treatment	Day 1 time	Results				
		N	Mean (SD)	Median	Min	Max

Parameter Treatment	Day 1 time	Results				
		N	Mean (SD)	Median	Min	Max
Visual Analog Scale. Pain intensity						
OKITASK®	0 min. Baseline	xx	xx.x (xx.x)	xx.x	xx.x	xx.x
PLACEBO	0 min. Baseline	xx	xx.x (xx.x)	xx.x	xx.x	xx.x
$\mu_T - \mu_R$ 95% CI			xx.x [xx.x; xx.x]			
OKITASK®	5 minutes	xx	xx.x (xx.x)	xx.x	xx.x	xx.x
PLACEBO	5 minutes	xx	xx.x (xx.x)	xx.x	xx.x	xx.x
$\mu_T - \mu_R$ 95% CI			xx.x [xx.x; xx.x]			
...						
OKITASK®	6 hours	xx	xx.x (xx.x)	xx.x	xx.x	xx.x
PLACEBO	6 hours	xx	xx.x (xx.x)	xx.x	xx.x	xx.x
$\mu_T - \mu_R$ 95% CI			xx.x [xx.x; xx.x]			

Figure 12.1 Secondary efficacy. Visual Analogue Scale. Pain Intensity profile. ITT population. N = XX

[figure not shown]

Figure 12.2 Secondary efficacy. Visual Analogue Scale. Difference in Pain Intensity means with 95% CI. ITT population. N = XX

[figure not shown]

Table 12.16 Secondary efficacy. Visual Analogue Scale. Pain Relief profile. ITT population. N = XX

Parameter	Treatment	Day 1 time	Results				
			N	Mean (SD)	Median	Min	Max
Visual Analog Scale. Pain relief							
OKITASK [®]	0 min. Baseline	xx	xx.x (xx.x)	xx.x	xx.x	xx.x	xx.x
PLACEBO	0 min. Baseline	xx	xx.x (xx.x)	xx.x	xx.x	xx.x	xx.x
$\mu_T - \mu_R$	95% CI		xx.x [xx.x; xx.x]				

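### The primary AUC0-6h model is left open by an optional covariate clause, and time-0 pain VAS, already collected, is not assured a place in it

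*SAP*

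**What the plan says.** Section 10.1 sets the base analysis: "Treatment AUCs will be compared using ANOVA methodology (simple GLM model"). The next sentence opens it up: "In case of significant covariates discovered during baseline data analysis, such covariates could be added to the ANOVA model (level to stay 0.15"). The decision then rests on the result: "F-test for type III treatment effect will be used for testing the Null hypothesis". Superiority also requires the OKITASK mean AUC to be the lower one, without saying whether raw or adjusted means are read.

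Section 9.2 plans between-group comparisons for two variables only: gender and "Age (ANOVA from LME model"). These are the natural candidates for the covariate clause.

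Time-0 pain is available. Section 3.2 has it measured immediately before dosing ("The patient will assess pain by VAS at 0" minutes), a footnote to section 8.1 defines it as baseline, and section 10.1 starts the AUC from it: "pain intensity profile between time 0 (baseline value of VAS) and 6 hours post-treatment". Its between-arm difference appears only in the secondary profile table, 12.15, in the rows labelled "0 min. Baseline".

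Section 6 sizes the trial on unadjusted AUC: "values for placebo and ketoprofen were about 263 and 173" mm h, with SD 121, difference 90, 29 per group and 70 enrolled.

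**The concern.** Two things are at stake.

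- **Precision.** Baseline pain is the only pre-dose measurement on the endpoint's own scale. If it predicts AUC0-6h, leaving it out widens the confidence interval and lowers power. Its presence in the AUC does not do the work of adjustment: under the trapezoidal rule and the scheduled times, the time-0 value carries 2.5 of 360 minutes, about 0.7% of the weight.
- **A deciding model that is not fixed.** The clause does not say which covariates are candidates, whether significance means imbalance between arms or association with AUC, or whether adding is required once the criterion is met. Different analysts could follow it faithfully and report different primary p-values. If the choice is made after the results are seen, the type I error is no longer the nominal one.

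**Working it through.** **Inputs.** Difference 90 mm h, SD 121 mm h, two-sided alpha 0.05, 29 evaluable and 35 enrolled per arm (section 6). The correlation rho between time-0 VAS and AUC0-6h is not given; 0 to 0.5 is an assumed range.

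**The plan's own figure.** n per arm = 2 × (1.960 + 0.842)² × 121² / 90² = 28.4, so 29 per arm and 58 in total. Dropout: 29 / 0.85 = 34.1, so 35 per arm and 70 in total. Both reproduce. At 29 per arm the normal approximation gives 80.8% power and the noncentral t (56 df) gives 79.5%; the latter is used below.

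**Power with time-0 VAS as a fixed covariate.** The residual SD is 121 × √(1 − rho²), with 2n − 3 df. Chance baseline imbalance multiplies the variance of the treatment difference by 1 + t²/(2n − 2), where t follows a t distribution with 2n − 2 df. Power was averaged over that distribution.

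| rho | 29 per arm, simple formula | 29 per arm, averaged over imbalance | 35 per arm, averaged |
|---|---|---|---|
| unadjusted | 79.5% | 79.5% | 86.6% |
| 0 | 79.5% | 78.7% | 86.1% |
| 0.1 | 79.9% | 79.1% | 86.4% |
| 0.2 | 81.1% | 80.4% | 87.4% |
| 0.3 | 83.1% | 82.4% | 89.1% |
| 0.5 | 89.5% | 88.9% | 94.0% |

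The break-even correlation is 0.14 at 29 per arm and 0.12 at 35.

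**Precision at 29 per arm.** The mean variance factor is (1 − rho²) × (2n − 3)/(2n − 4):

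- rho 0.3: 0.91 × 55/54 = 0.927. The 58 adjusted patients are worth 58 / 0.927 ≈ 63 unadjusted.
- rho 0.5: 0.75 × 55/54 = 0.764. They are worth 58 / 0.764 ≈ 76.
- The 95% CI half-width is 2.003 × 121 × √(2/29) = 63.7 mm h unadjusted. It falls to 61.3 at rho 0.3 and 55.7 at rho 0.5.

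**Type I error.** 50,000 null trials were simulated per rho, with 29 per arm and age and gender unrelated to AUC. A trial counts as a rejection when two-sided p < 0.05 and OKITASK is lower, so the nominal rate is 2.5%. Monte Carlo SE is 0.07 to 0.09 points.

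| How the clause is applied | rho 0 | rho 0.3 | rho 0.5 |
|---|---|---|---|
| Age and gender, best of four models | 3.2% | 3.0% | 3.0% |
| Age, gender and time-0 VAS, best of eight models | 3.4% | 3.8% | 4.5% |

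Across the same three correlations, mechanical use gives:

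- Age and gender, added if unbalanced at p < 0.15: 2.5-2.6%
- Age and gender, backward selection at 0.15: 2.7-2.8%
- Age, gender and time-0 VAS, backward selection at 0.15: 2.7-2.8%
- Fixed ANCOVA with time-0 VAS: 2.5-2.6%

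**The case against.** The strongest reply is that an unadjusted ANOVA is a legitimate choice. It is valid, it agrees with a sample size built on unadjusted AUC, and preferring ANCOVA does not make the plan wrong. That stands, and no claim is made that the trial is underpowered or the test invalid.

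The gain also depends on a correlation the SAP does not give. Below 0.14 adjustment loses a little power, and the 30 mm entry threshold in section 3.1 may narrow the baseline range and push the correlation low. That stands too.

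Section 6 is already cautious, because it uses the larger of its two SDs. With the equal-weight pooled SD, √((106² + 121²)/2) = 113.7, unadjusted power is 84.2% at 29 per arm and 90.4% at 35. This slack softens the need for more precision but does not settle which model decides.

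Finally, the higher error rates suppose that someone fits every subset and reports the most favourable. The SAP does not plan that, and mechanical readings of the 0.15 rule add at most about 0.3 points. This is fair. But the wording is permissive rather than mechanical, and nothing in it rules out such a choice. Even a sponsor who prefers the unadjusted test needs to remove the clause.

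**Conclusion.** The point holds. The primary model is not fixed, and time-0 VAS is not assured in it although every AUC already needs that value.

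The effect on power is lopsided in favour of adjusting. At 29 per arm and rho 0 the cost is 0.8 points; at rho 0.3 and 0.5 the gain is 2.9 and 9.4 points (79.5% to 82.4% and 88.9%). These figures rest on delta 90, SD 121 and an assumed correlation.

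The type I error risk is the smaller matter. It is about half a point if age and gender are the only candidates and the best model is picked. It reaches up to 2 points (4.5% against 2.5%) only if time-0 VAS is also optional, which the wording neither requires nor excludes. This should be corrected, but it does not invalidate the planned test.

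**What to change.** Before unblinding, delete the optional covariate sentence in section 10.1 and replace it with wording such as:

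> AUC0-6h will be analysed by ANCOVA with treatment as factor and time-0 pain-intensity VAS as covariate, plus any stratification factor used in the randomisation. No term will be added or removed on the basis of the data. The type III F-test for treatment in this model is the primary test, and the direction condition is read on the adjusted mean difference.

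Use the same model for the LOCF, multiple-imputation and per-protocol analyses, and keep the unadjusted ANOVA as supportive. As a minor addition, report the adjusted difference with its 95% CI in Tables 12.9 to 12.12, which now show arm summaries and a p-value (12.11 and 12.12 repeat 12.9 and 12.10). Site is a term in the secondary model of section 10.2; whether it also belongs in the primary model should be decided and written down at the same time.

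The cost is SAP wording, one model term with one residual degree of freedom, and one table row. At 29 per arm, power falls by 0.8 points if baseline pain is unrelated to AUC. No patient is lost, no new data are needed and N is unchanged. If the protocol, not at hand here, also states the primary model, it must be brought into line.

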10.2 SECONDARY EFFICACY

Secondary efficacy variables will be analyzed only for ITT population.

¹ Clinically significant

AUC_{0-6h} without or with LOCF of pain relief profile between time 0 (baseline value of VAS) and 6 hours post-treatment. AUC_{0-6h} analysis will be based on **actual rather than scheduled timings** and will be calculated using the trapezoidal rule (see as per primary variable).

Pain profile – Pain intensity profile will be analyzed using Analysis of Variance (ANOVA) for repeated measurements. The model will include fixed effect terms for clinical site, time point and treatment. Time point will be specified as a repeated measurement. In order to select an appropriate matrix for the observations within each subject, 3 models will be fitted using the compound symmetry, Huynh-Feldt and unstructured structures. The matrix for the final model will be selected using Akaike's Information Criterion where the lowest value indicates the best fit. The importance of the treatment-by-site interaction will be investigated but if the term is not significant at the 10% level, it will be excluded from the final model. The adjusted least squares mean will be estimated for each combination of time point and treatment. The estimated treatment difference between OKITASK® and placebo at each time point will be presented together with the corresponding 95% confidence interval. Pain profile will be analyzed based on **scheduled rather than actual timings**.

SAS code example:

```
proc mixed data=locf method=REML order=internal1;
  class patid site trt time;
  model pain = trt time trt*time
    site trt*site/ intercept ddfm=satterth;
  repeated time/ type=CS2 subject=patid(trt);
  lsmeans trt*time/ diff=all cl;
run;
```

Pain relief – Pain relief will be analyzed in the same way.

LOCF replaced data of pain intensity and pain relief will be presented graphically by treatments and time points.

Time to first perceptible relief (TFPR)³ – Kaplan-Meier curve and Log rank test will be used to describe and test treatment profile differences. In table it will be presented with median, 95% CI and p-value from Log rank test.

Time to meaningful pain relief (TMPR)⁴ – Kaplan-Meier curve and Log rank test will be used to describe and test treatment profile differences. In table it will be presented with median, 95% CI and p-value from Log rank test.

Time to REMD – Time to rescue medication will be calculated for each subject and presented using only median value. If the number of subjects will be adequate Kaplan-Meier curve and Log rank test will be used to describe and test treatment profile differences.

Patient's overall assessment – will be described as nominal data (6 hours post-

¹ Data must be sorted!

² CS or HF or UN

³ CRF data

⁴ CRF data

dose). Mann-Whitney¹ test will be applied in order to test differences between treatments response.

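### Pain relief is not rated at time 0, yet the relief AUC0-6h starts from a baseline VAS value and Table 12.16 reports a 0 min relief row

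*SAP*

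**What the plan says.** SAP section 3.2 separates the two scales. At time 0 only pain is rated: "The patient will assess pain by VAS at 0' – immediately before study drug dosing". For relief it says "Pain relief will be assessed by VAS at" twelve times, the first at 5 minutes and the last at 360 minutes. A footnote in section 9.2 fixes the reference point: "Baseline is Day 1 time 0 minutes".

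Section 10.2 defines the secondary AUC0-6h "of pain relief profile between time 0 (baseline value of VAS) and 6 hours post-treatment", which "will be calculated using the trapezoidal rule (see as per primary variable". The wording matches that of the primary pain-intensity AUC in section 10.1, where the baseline VAS exists and is on the right scale.

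For the time profile, section 10.2 sets out a repeated-measures model for pain intensity. Compound symmetry, Huynh-Feldt and unstructured covariances are all fitted, the lowest AIC decides, and a treatment difference with 95% CI is given at each time point. Relief gets one sentence: "Pain relief will be analyzed in the same way".

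Table 12.16, titled "Secondary efficacy. Visual Analogue Scale. Pain Relief profile. ITT population", opens with a 0 min baseline row holding N, mean (SD), median, minimum and maximum for each arm, and a between-arm difference with 95% CI.

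The SAP nowhere sets relief at time 0 to a value, and nowhere says that time 0 is left out of the relief analyses.

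**The concern.** The trapezoidal rule needs a relief value at time 0, and the example table asks for one by arm, but none is collected. Whoever programs the analysis has to supply a convention, and the conventions differ in effect.

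- **Use the baseline VAS as section 10.2 names it.** A pain score then stands on the relief scale. The two scales run in opposite directions, so the patient in most pain starts with the most relief.
- **Set relief to 0 for everyone.** This makes sense for the AUC. A constant carried into the repeated-measures model, however, has no variance, and the planned covariance selection cannot cope with that.
- **Leave time 0 missing.** The model runs on 12 times, but the AUC has no starting value and the 0 min row stays empty.

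The time profile of pain relief is a named secondary objective (section 5.2). Its starting convention and covariance model should be settled before unblinding.

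**Working it through.** The SAP gives no numerical figure for pain relief, so there is none to reproduce. Its sample-size calculation concerns pain intensity and is not involved.

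**Inputs**
- Relief times: 5, 10, 15, 30, 45, 60, 90, 120, 180, 240, 300 and 360 min, which is 12 points (section 3.2). Adding time 0 makes 13.
- VAS range 0-100 mm (Table 3.1); randomization requires at least 30 mm (section 3.4). I assume that the time-0 score also meets this threshold, so it lies in 30-100 mm. The SAP does not guarantee this, because the entry rating may precede the time-0 rating.
- 35 patients per arm (section 3.2).

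**1. Baseline intensity used as relief at time 0**

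Compared with a starting value of 0, an intensity P0 changes only the first trapezoid, by P0/2 × 5/60 h.
- P0 = 30: 30/2 × 5/60 = 1.25 mm·h.
- P0 = 100: 100/2 × 5/60 = 4.17 mm·h.

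The relief AUC can reach 100 × 6 = 600 mm·h, so the shift is 0.2% to 0.7% of the scale. P0 is measured before dosing in randomized arms, so its expected contribution is the same in both and cancels from the treatment difference.

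If the 5 min relief score were also missing and filled with P0, the excess over zero at both times would be P0 × 5/60 + P0/2 × 5/60, which is 3.75 to 12.5 mm·h. This applies only under the wider reading of section 7.1 discussed below.

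**2. Relief set to 0 at time 0 and kept in the model**

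*Unstructured.* Every time-0 residual is zero, so the first row and column of the 13 × 13 covariance are zero. In an illustrative data set (35 per arm, time 0 fixed at 0) the matrix had rank 12 and log-determinant minus infinity; the 12 × 12 post-dose block had full rank. With 70 − 2 = 68 degrees of freedom, a time-0 variance v contributes 68 × ln(v) to −2 log-likelihood: −313 at v = 0.01 and −1253 at v = 10⁻⁸. This falls without limit, while the AIC penalty for 13 × 14/2 = 91 parameters stays at 182. The lowest AIC therefore has no meaning.

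*Huynh-Feldt.* The covariance of times i and j is (σi² + σj²)/2 − λ. A zero variance at time 0 requires zero covariance with each later time, so σj²/2 − λ = 0, that is σj² = 2λ at every post-dose time. All post-dose variances are then equal, and their correlation is λ/2λ = 0.5, whatever the data show.

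*Compound symmetry.* This can be fitted. Its common variance is the average of the time-specific variances, so a zero row multiplies it by 12/13 and the standard error by √(12/13) = 0.961. The illustration agrees: 389.1/421.6 = 0.923, and CI half-width 9.24 against 9.62 mm. It also attaches the ±9.24 mm interval to time 0, where nothing varies.

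How far these standard errors are from the truth depends on the variance pattern.
- Equal post-dose variances: about 4% too small at every post-dose time.
- Rising variances (assumption: SD from 8 to 28 mm in equal steps over the 12 times): mean variance = 18² + (20/11)² × (12² − 1)/12 = 363.4. With the zero row it is 363.4 × 12/13 = 335.4, a pooled SD of 18.3 mm. At 5 min the standard error is 18.3/8 = 2.3 times the correct one; at 360 min it is 18.3/28 = 0.65 of it.

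Without the zero row the pooled SD is √363.4 = 19.1 mm, giving ratios of 2.4 and 0.68. Most of the error in the rising case therefore comes from being confined to compound symmetry, and the zero row adds the factor 0.961.

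**3. The 12 measured times only**

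The covariance has full rank, the unstructured model has 12 × 13/2 = 78 parameters, and all three structures can be compared.

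**The case against.** The strongest reply is that relief is not collected at time 0, so no time-0 record exists, the mixed model omits missing responses, and it runs on the 12 measured times. The SAP prescribes neither setting relief to 0 nor putting intensity into the model. Section 12 holds table examples, and its footnote allows the report's tables to differ from them, so an empty row can be dropped. The slip looks like intensity wording carried over to relief.

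Much of this stands. A reader might infer that the relief model must fail. The documents do not support that: time 0 in the model is suggested by the instruction to treat relief like intensity and by Table 12.16, but is not stated. A reader might also infer that the relief comparison is biased. That does not follow, since the AUC shift is small and expected to be equal in both arms. A flat 4% understatement of standard errors is not general either; it needs time 0 kept at 0, compound symmetry chosen and equal post-dose variances.

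Baseline carry-forward is likewise only a possible reading. Section 7.1 mentions secondary variables, but it stands under the primary efficacy heading, refers to a missing pain score, and rests on data that decrease over time, which describes intensity. Carrying forward normally uses a variable's own earlier value, and relief has none before dosing.

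The reply does not rescue the AUC. Section 10.2 names a starting value that is on the wrong scale, and leaving time 0 missing gives the trapezoidal rule nothing to start from.

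**Conclusion.** Wrong as written, minor severity. The contradiction is in the text: relief is first rated at 5 minutes, but its AUC and its example table require a value at time 0.

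The literal reading shifts each relief AUC by 1.25 to 4.17 mm·h, assuming a time-0 intensity of 30 to 100 mm, with no expected effect on the treatment difference. The modelling consequence is conditional: if relief is fixed at 0 and time 0 is kept in the model, the unstructured fit is singular and the AIC selection is invalid. The resulting error in the standard errors depends on a variance pattern that the SAP does not give.

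Only the secondary relief analyses are affected. The primary pain-intensity AUC has a proper time-0 measurement and is unchanged.

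**What to change.** Amend the SAP in four places:

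1. Section 10.2, relief AUC: state that relief at time 0 is 0 mm by definition and is used only to start this AUC. Remove the reference to the baseline VAS.
2. Section 10.2, relief profile: state that the model is fitted to the 12 post-dose times.
3. Table 12.16: delete the 0 min row.
4. Section 7.1: state that baseline carry-forward applies to pain intensity only.

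The cost is a few lines of SAP text and one filter in the analysis program. Data collection, sample size and the primary analysis do not change.

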3. STUDY DESIGN

This is a multicenter, double-blind, randomized, parallel groups, placebo-controlled study to assess the efficacy and safety of OKITASK® 40 mg granules in patients with acute pain syndrome after removal of molar teeth. The study will be conducted at 3-6 Russian sites. A total expected number of enrolled subjects is 70 (35 per each group). Patients' enrollment to the sites is competitive.

The study will consist of three periods: screening, study treatment and follow-up.

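### A 10% pre-test on treatment-by-site decides how sites are weighted in the secondary pain-profile differences; with unequal sites, the 95% intervals under-cover when the term is kept (minor)

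*SAP*

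**What the plan says.** SAP section 10.2 analyses the pain-intensity profile with a repeated-measures model containing site, time point and treatment. Treatment-by-site is to be examined, and "if the term is not significant at the 10% level, it will be excluded from the final model"; so at p<0.10 it stays.

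The SAS example puts the interaction in the same MODEL statement ("site trt*site/ intercept ddfm=satterth") that feeds "lsmeans trt*time/ diff=all cl". No observed-margins option is given. What is reported comes from that model: "The estimated treatment difference between OKITASK® and placebo at each time point will be presented together with the corresponding 95% confidence interval". The second profile follows suit: "Pain relief will be analyzed in the same way". The results fill Tables 12.15 and 12.16 and Figures 12.2 and 12.4.

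On sites, section 3 states "The study will be conducted at 3-6 Russian sites" and "Patients' enrollment to the sites is competitive", with 70 patients in total. The SAP gives no pooling rule for small sites, no weights for the site average and no fallback for a site that lacks one arm.

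**The concern.** A test on the trial's own data chooses between two estimators. Without the interaction, sites contribute according to the information they carry. With it, default LS means give each of S sites weight 1/S, so a small site counts as much as a large one.

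The term is kept exactly when the site-specific differences happen to disagree, which is also when the equal-weight average moves furthest from the information-weighted one. The reported interval ignores that selection. If effects truly differ between sites, the two models also estimate different averages, so the data decide which quantity is reported. At stake are all the between-group differences in the two secondary profiles.

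**Working it through.** **Inputs.** From the SAP: 3-6 sites, competitive enrolment, 70 patients allocated 1:1, 10% retention level, 95% intervals. Assumed, because the SAP does not give them: the site sizes, unstratified allocation and the within-patient correlation. Simulations are of the between-patient part, with no true interaction unless stated.

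**1. The plan's own sample size.** With the difference of 90, SD 121, two-sided 0.05 and 80% power: n = 2 × (1.960 + 0.842)² × 121² / 90² = 28.4, so 29 per arm and 58 in total. Allowing 15% drop-out, 29/0.85 = 34.1, so 35 per arm and 70 in total. This reproduces section 6, and the present point does not touch it.

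**2. Site weights.** Without the interaction, a site's weight is proportional to n1·n2/(n1+n2). With balanced arms that is n_s/N. In a 36/20/10/4 split the smallest site has 4/70 = 5.7%. With the interaction kept it has 1/4 = 25%.

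**3. Standard error.** With balanced arms and unit variance, the variance is Σ(4/n_s)/S² with the term and 4/N = 4/70 = 0.0571 without it. For 40/20/6/4: 4 × (0.025 + 0.050 + 0.1667 + 0.250)/16 = 0.1229, and √(0.1229/0.0571) = 1.47. The other splits are computed in the same way.

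| Assumed split | SE ratio by formula | Interval width in kept trials | Overall coverage with the rule | Kept and non-estimable, all trials |
|---|---|---|---|---|
| 35/21/14 | 1.07 | +4% | 94.2% | 0% |
| 30/20/12/8 | 1.13 | +11% | 94.4% | 0% |
| 28/18/10/6/4/4 | 1.29 | +28% | 94.0% | 1.75% |
| 40/20/6/4 | 1.47 | +48% | 93.5% | 1.1% |

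The last three columns are simulated. Simulated widths differ from the formula because the residual variance is smaller with the term in the model and arms are not exactly balanced within sites. A repeat of the simulation agreed to within simulation error (about +50% for the last split).

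**4. How often, and coverage.** The term was kept in 9.5-11.5% of simulated trials, as a 10% test implies. With a true site-effect SD of half the residual SD it was kept in 28-37%. Among kept trials without interaction, coverage was about 91% for the mildest split and about 81% for the worst, although the intervals were wider. Without the rule it was about 95%.

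**5. Near-equal sites.** For 24/23/23 the width ratio in kept trials is about 0.97. Equal and information weights nearly coincide, so the estimate hardly moves and overall coverage is almost unchanged.

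**6. Single time points.** Only the between-patient share of the variance is inflated. For +48% the variance ratio is 1.48² = 2.19. At correlation 0.5 the SE ratio is √(1 + 0.5 × 1.19) = 1.26, and at 0.8 it is √(1 + 0.8 × 1.19) = 1.40. For +4% (1.04² = 1.08) the same steps give about 1.02 and 1.03.

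**7. Estimability.** In the design matrix of the printed model (13 time points), one site with a single arm makes the LS-mean differences non-estimable with the interaction and leaves them estimable without it. Failure needs both retention and such a site. Among kept trials the share with a one-arm site was 0%, 1%, 21% and 13% for the four splits; times about 10% retention, that is about 0%, 0.1%, 2% and 1% of all trials, in line with the table. A harsher split would raise this: for 36/14/8/6/4/2 the chance of a one-arm site is 57%, so roughly 0.57 × 0.10 = 6% if the two events were independent.

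**The case against.** The rule is written in advance with its threshold, the code is labelled an example, and an equal-site average is a defensible summary when effects truly differ. The affected tables carry differences with intervals and no p-values, and no success decision rests on them. A non-estimable LS mean is flagged by the software, so it cannot pass unnoticed. Averaged over all trials, the coverage loss is about 1.5 percentage points at most. All of this stands, and it is why the point is minor.

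It does not remove the defect. Prespecifying a pre-test does not correct the intervals that follow it, and the prose itself, not only the code, sends a retained interaction into the final model without stating weights.

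Several stronger readings are tempting, and the SAP does not support them:

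- **The intervals always widen.** They do so only with unequal sites. Competitive enrolment permits unequal sites but does not quantify them.
- **Loss of the whole profile is likely.** It needs two events together, and even a one-patient site causes it only if the term is kept.
- **Allocation is unstratified because the SAP mentions no stratification.** That detail is commonly left to the protocol, and stratifying by site would make one-arm sites rarer.
- **The time-0 reading distorts the interaction test.** The term is constant over time and Table 12.15 lists baseline, but that is one of 13 readings and its effect has not been quantified.

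**Conclusion.** The point holds at minor severity. As written, a data-driven test can switch all pain-intensity and pain-relief differences to equal site weights, in about 10% of trials when there is no interaction. When it does so with unequal sites, the 95% label is wrong: coverage is about 91-81% in those trials and about 93.5-94.4% overall, under assumed splits from 35/21/14 to 40/20/6/4. With near-equal sites there is practically no harm. Non-estimability is a secondary risk, about 0-2% of trials under the same splits with unstratified allocation.

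A reader might infer that the primary conclusion is exposed. It is not: section 10.1 compares the AUC with a simple GLM that has no planned site term, and the sample size does not depend on this model.

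**What to change.** In section 10.2, take the LS-mean differences and intervals for both profiles from one fixed model with treatment, time, treatment-by-time and site. Delete the 10% retention rule, and remove `trt*site` from the model that produces the LS means. Report the treatment-by-site p-value and the site-specific differences as a separate exploratory check.

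The cost is about two lines of text and code. There is one real downside: if heterogeneity is genuine, the headline difference reflects the site sizes that enrolment happened to produce and is no longer an equal-site average. The separate output still shows the heterogeneity.
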